6.1 Variables

Corporate Confidential Information

6.2 Descriptive analyses

6.3 Graphical presentation of results

Corporate Confidential Information

6.4 Pharmacokinetic / pharmacodynamics interactions

The relationship between PK and key PD parameters may be explored using a graphical approach. Descriptive statistics may be provided.

1tormation

7 Statistical methods for Pharmacodynamic (PD) parameters

7.1 Analysis of the primary variables

The first primary variables are adverse events, vital signs (blood pressure, pulse rate, body temperature), ECG intervals and laboratory measurements.

The second primary variable will be the change in the 12 hour average of SBP measured by ABPM 28 days following the start of treatment.

7.1.1 Variable

The primary safety variables are defined in Section 8, below.

The primary efficacy variable is defined as the 12 hour daytime average SBP on day 28 minus the 12 hour daytime average SBP on day -1.

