Data analysis	
The primary efficacy variable will be the change in the 12 hour average of systolic blood pressure measured by ambulatory blood pressure monitoring (ABPM) 28 days following the start of treatment. Out-of-office ABPM is a more reliable measure of a patient's blood pressure than office-based BP readings which may be falsely elevated because of "white-coat" phenomena (Bakris et al 2010). The change from baseline in the placebo group will be compared to the change from baseline in the pooled LHW090 doses. The criteria to demonstrate efficacy (success) will be based on statistically significant (1-sided <math>p<0.1</math>) greater reduction from baseline in mean daytime SBP with active treatment (pooled doses) than with placebo, as well as an estimated median reduction on active treatment (pooled active doses) of at least 7 mmHg higher than on placebo. The threshold of a 7 mmHg reduction in placebo-adjusted systolic BP by ABPM is considered clinically significant since similar magnitude changes were observed in a phase 3 trial of an endothelin-receptor antagonist, darusentan, for the same indication (Weber et al 2009).
 
Study patients will be randomized into one of 3 groups, placebo, 100 mg LHW090 and 200 mg LHW090, as an add-on therapy to conventional background anti-hypertensive therapy. 40 patients will be randomized to placebo, and 20 to each dose of active treatment. This will give around 32 completers in the placebo group and 16 on each active dose group. The primary analysis of change in mean daytime systolic blood pressure will be performed using the data collected during the period 0900 to 2100 consistent with recommendations from the European Society for Hypertension (O'Brien et al 2013). The average of these 12 hours of data will be produced using data from the baseline ambulatory blood pressure monitoring on Day -2 and Day 27.
 
The change from baseline in mean daytime SBP will be estimated from a longitudinal model using all data collected for every patient until Day 27. The model will include fixed effects for baseline, treatment (including dose), and visit, and a random effect for each subject. This analysis is unbiased under the assumption that the data are missing at random (MAR).

Key words	Resistant hypertension

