### 3      Investigational plan

#### 3.1    Study design

This is a non-confirmatory, randomized, sponsor open, site and subject blind, parallel group, placebo-controlled study to evaluate the safety and efficacy of 4 weeks once daily treatment with LHW090 in patients with resistant hypertension. Patients with uncontrolled hypertension defined as a mean daytime systolic blood pressure  $\geq 135$  mmHg by ambulatory blood pressure monitoring (ABPM) on a stable (at least 1 month) regimen of optimal doses of an angiotensin receptor blocker (ARB) plus a diuretic plus at least one additional class of anti-hypertensive medication will be considered for this trial (Weber et al 2014; Vongpatanasin 2014; Calhoun et al 2008). Patients with resistant hypertension will be randomized to either placebo or 1 of 2 dose regimens of LHW090, i.e. LHW090 100 mg once daily, LHW090 200 mg once daily, as an add-on to their anti-hypertensive regimen at baseline.

[figure not shown]
Each patient will participate in an approximately 3 week screening period, a 2-week single blind placebo run-in period, baseline assessments, a 4 week treatment period, and an end of study assessment (Figure 3-1). During the 2 week placebo run-in period, patients will receive regular reminders by the site to be compliant with their anti-hypertensive medications. At the end of this run-in period, patients who demonstrate  $\geq 80\%$  compliance with placebo will be randomized. Compliance will be established by pill count and review of medication diary. Patients will be advised that study entry cannot be fully determined until the completion of the run-in period.

On Day -2, patients will commence 24 hour ABPM monitoring and return the next day (Day -1) to have the ABPM device removed and the data collected. Patients may have additional attempts to complete a successful ABPM assessment (defined by satisfactory BP data sampling over the 24 hours and standards for device quality check) if the previous attempts are unsuccessful (O'Brien et al 2013). Upon collection of satisfactory baseline ABPM assessment, patients will then return for baseline pharmacodynamic assessments on Day -1 and then begin active treatment on Day 1. Patients will be randomized in a 1:1:2 fashion to either:

- LHW090 100 mg once daily for 28 days
- LHW090 200 mg once daily for 28 days
- Matching placebo for 28 days

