Patients have the option to return on Day 3 for vital signs. Patients will then visit the clinic at weekly intervals (Day 7, 14 and 21) for safety, PK, and PD assessments. On visit days, patients will be instructed to take their medications at the site. On Day 27, patients will commence a final 24 hour ABPM assessment and then return the next day to have the device removed and then begin collection of Day 28 steady-state PK and PD assessments. As stated above, patients may have additional attempts to complete a successful ABPM assessment (defined by satisfactory BP data sampling over the 24 hours and standards for device quality check) at the Sponsor's discretion if previous attempts are unsuccessful (O'Brien et al 2013). Patients will be asked to return after approximately 1 week for end of study (EOS) assessments.

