### 11.4.1 Variable(s)

The primary efficacy variable will be the change in the 12 hour average of systolic blood pressure measured by ambulatory blood pressure monitoring (ABPM) 28 days following the start of treatment. This is defined as the 12 hour daytime average systolic blood pressure on day 28 minus the 12 hour daytime average systolic blood pressure on day -1.

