### 11.4.2 Statistical model, hypothesis, and method of analysis

The primary efficacy variable will be the change in the 12 hour average of systolic blood pressure measured by ambulatory blood pressure monitoring (ABPM) 28 days following the start of treatment. Out-of-office ABPM is a more reliable measure of a patient's blood pressure than office-based BP readings which may be falsely elevated because of "white-coat" phenomena (Bakris et al 2010). The change from baseline in the placebo group will be compared to the change from baseline in the **pooled** LHW090 doses. The criteria to demonstrate efficacy (success) will be based on statistically significant (1-sided  $p<0.1$ ) greater reduction from baseline in mean daytime SBP with active treatment (pooled doses) than with placebo, as well as an estimated median reduction on active treatment (pooled active doses) of at least 7 mmHg higher than on placebo. The threshold of a 7 mmHg reduction in placebo-adjusted systolic BP by ABPM is considered clinically significant since similar magnitude changes were observed in a phase 3 trial of an endothelin-receptor antagonist, darusentan, for the same indication (Weber et al 2009).

Study patients will be randomized into one of 3 groups, placebo, 100 mg LHW090 and 200 mg LHW090, as an add-on therapy to conventional background anti-hypertensive therapy. 40 patients will be randomized to placebo, and 20 to each dose of active treatment. This will give around 32 completers in the placebo group and 16 on each active dose group. The primary analysis of change in mean daytime systolic blood pressure will be performed using the data collected during the period 0900 to 2100 consistent with recommendations from the European Society for Hypertension (O'Brien et al 2013). The average of these 12 hours of data will be produced using data from the baseline ambulatory blood pressure monitoring on Day -2 and Day 27. The change from baseline in mean daytime SBP will be estimated from a longitudinal model using all data collected for every patient until Day 27. The model will include fixed effects for baseline, treatment (including dose), and visit, and a random effect for each patient. This analysis is unbiased under the assumption that the data are missing at random (MAR).

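### Do the two day pairs for the primary blood pressure variable (Day 28 and Day -1, or Day 27 and Day -2) give two different endpoints?

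*SAP*

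**What the plan says.** Two places define the variable on one pair of days. In SAP 7.1.1 (Variable) it is "defined as the 12 hour daytime average SBP on day 28 minus the 12 hour daytime average SBP on day -1". Protocol 11.4.1 (Variable(s)) has the same pair: "12 hour daytime average systolic blood pressure on day 28 minus the 12 hour daytime average systolic blood pressure on day -1". Neither gives a clock window.

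Two other places use the days just before. Protocol 11.4.2 obtains the 12-hour averages "using data from the baseline ambulatory blood pressure monitoring on Day -2 and Day 27" and fits the longitudinal model "using all data collected for every patient until Day 27". The data analysis row of the synopsis says the same of the averages: "produced using data from the baseline ambulatory blood pressure monitoring on Day -2 and Day 27". Both places set the daytime window at 0900 to 2100.

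Protocol 3.1 describes how the readings arise. At baseline: "On Day -2, patients will commence 24 hour ABPM monitoring and return the next day (Day -1) to have the ABPM device removed". At the end of treatment: "On Day 27, patients will commence a final 24 hour ABPM assessment and then return the next day to have the device removed". At both points "patients may have additional attempts to complete a successful ABPM assessment" if an earlier attempt fails. Success is judged on adequate sampling over the 24 hours and on the device quality check.

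**The concern.** The endpoint that drives the success rule should have one definition, and here adjacent protocol sections name different days. Read literally, the model stops at Day 27 while the variable is defined on Day 28. The SAP is the document a programmer works from, and its visible definition gives only the later pair and no window.

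If someone selected readings by calendar study day, Day 28 would contain only the tail of the final recording. For a device fitted in the morning, that tail holds little or none of the daytime window. The primary variable could then be missing, or be averaged over the wrong hours, in a comparison that rests on about 32 placebo and 32 pooled active completers. Because repeat recordings are allowed, a bare day number also need not identify the recording that was accepted.

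**Working it through.** The plan gives no figure to reproduce here. The check sets the passages side by side and then does clock arithmetic.

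**1. The recordings that exist (protocol 3.1).**

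| Time point | Device fitted | Device removed, data collected | Label in protocol 11.4.2 and synopsis | Label in protocol 11.4.1 and SAP 7.1.1 |
|---|---|---|---|---|
| Baseline | Day -2 | Day -1 | Day -2 | Day -1 |
| End of treatment | Day 27 | Day 28 | Day 27 | Day 28 |

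The earlier pair matches the fitting days and the later pair matches the removal days, at both ends. Protocol 3.1 describes no second recording at either time point, apart from repeats after an unsuccessful attempt. The two labels therefore have only one recording to refer to.

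**2. Is any of the window lost?** Let the device be fitted at clock hour *f* on the first day, so that the recording runs from *f* to *f* + 24 h. The hours of the 0900 to 2100 window on each calendar day are:

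- second day (Day 28 or Day -1): min(12, max(0, *f* - 9))
- first day (Day 27 or Day -2): 12 minus that number

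The documents do not state the fitting hour, so the values of *f* below are assumed.

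| Fitting hour *f* | First day | Second day | Whole recording |
|---|---|---|---|
| 09:00 or earlier | 12 h | 0 h | 12 h |
| 10:00 | 11 h | 1 h | 12 h |
| 12:00 | 9 h | 3 h | 12 h |
| 15:00 | 6 h | 6 h | 12 h |
| 21:00 or later | 0 h | 12 h | 12 h |

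The last column is always 12 of 12. Taking the 0900 to 2100 readings from the recording, as protocol 11.4.2 says, gives the same average whichever day labels the recording.

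**3. What would selection by calendar day do?** For any fit between 09:00 and 21:00, neither calendar day holds the full window. At 12:00, for example, Day 28 alone gives 3 h and Day 27 alone gives 9 h. Consistent day labels would not remove this hazard, so it does not come from the mismatch.

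**4. Are the day numbers meant literally?** Protocol 11.4 also places the measurement 28 days after treatment starts. With treatment starting on Day 1, Day 27 is 27 - 1 = 26 days later and Day 28 is 28 - 1 = 27 days later, so neither fits exactly. Table 8-1 puts tolerance windows around visits, and SAP 7.1.2 summarises the ambulatory data by visit and time. The day numbers work as nominal visit labels, not as filters on date.

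**The case for a change.** The best case for amending the text is that the conflict is real, lies in current wording, and concerns the primary endpoint. No visible sentence says that Day 28 and Day -1 mean the recordings begun the day before. The study is open to the sponsor, so a question left to the derivation stage could be settled by people who can see treatment allocation. Two sentences would close it.

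The first part stands: the labels differ, and harmonising them would be tidier. The rest carries less weight. SAP 1.1 says the SAP implements the analysis planned in the protocol, so SAP 7.1.1 is read together with protocol 11.4.2, which names both the recordings and the window. That leaves an unblinded analyst little to choose: one accepted recording per time point and a fixed clock window. At baseline the patient proceeds only once a satisfactory recording exists. At the end of treatment a repeat follows an unsuccessful attempt, so the successful recording is the natural one to analyse. The sponsor does have discretion over whether a late repeat is made, but that is a separate matter and aligning the day labels would not touch it.

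A programmer who did filter on Day 28 would also find the daytime average empty for every device fitted by 09:00, which would be noticed at once. A later fit would give a partial average that is harder to spot, but step 3 of the working shows that this error would occur with either label.

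**Conclusion.** The inconsistency is clerical: the same two 24-hour recordings are named by start day in one place and by collection day in another. With the variable derived as protocol 11.4.2 describes, 0 of the 12 daytime hours are lost, and the estimate, its standard error, the power and the success rule are unchanged. No change to the plan is needed.

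This rests on three assumptions. Each time point has one accepted recording, as protocol 3.1 implies. The average is taken by clock time within that recording, not by calendar date. The parts of the SAP that cannot be seen, in particular the efficacy model in 7.1.3, do not say otherwise. The fitting hours in the working are assumed, but the conclusion does not depend on them, because the whole recording covers the window for every fitting hour.

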7.1.2 Descriptive analyses

The descriptive analyses of the safety variables are shown in the safety analyses in Section 8.

Summary statistics of the ABPM data and change from baseline data will be provided by treatment and visit/time.

7.1.3 Statistical model, assumptions and hypotheses

Analyses of the safety data will be descriptive, as shown in Section 8.

7.1.4 Handling of missing values/censoring/discontinuations

Missing data will not be imputed. The longitudinal repeated measures mixed model analysis method allows missing values.

7.1.5 Supportive analyses

Corporate Confidential Information

7.1.6 Graphical presentation of results

Arithmetic mean (SD) ABPM data will be plotted across time.

7.2 Analysis of the exploratory efficacy variables

Corporate Confidential Information

8 Statistical methods for safety and tolerability data

8.1.1 Variables

Adverse events, vital signs (blood pressure, pulse rate, body temperature), ECG intervals, laboratory measurements, as well as subject demographics, baseline characteristics, and treatment information.

8.1.2 Descriptive analyses

Subject demographics and other baseline characteristics

All data for background and demographic variables will be listed by treatment group and subject. Summary statistics (mean, standard deviation, minimum, median and maximum) will be provided by treatment group Corporate Confidential Information

Relevant medical history, current medical conditions, results of laboratory screens, drug tests and any other relevant information will be listed by treatment group and subject.

Treatment

Data for study drug administration (rescue medication) and concomitant therapies will be listed by treatment group and subject. The number and percentage of subjects completing treatment for each treatment group and cohort will be tabulated. For those not completing treatment, the reason for discontinuation will be listed by treatment group and subject.

Vital signs

All vital signs data will be listed by treatment, subject, and visit/time and if ranges are available abnormalities (and relevant orthostatic changes) will be flagged. Summary statistics will be provided by treatment and visit/time.

ECG evaluations

All ECG data will be listed by treatment, subject and visit/time, abnormalities will be flagged. Summary statistics will be provided by treatment and visit/time.

Clinical laboratory evaluations

All laboratory data will be listed by treatment, subject, and visit/time and if normal ranges are available abnormalities will be flagged. A separate listing is provided presenting all parameters in a subject with any abnormal values. Summary statistics will be provided by treatment and visit/time.

Adverse events

All information obtained on adverse events will be displayed by treatment and subject.

The number and percentage of subjects with adverse events will be tabulated by body system and preferred term with a breakdown by treatment. A subject with multiple adverse events within a body system is only counted once towards the total of this body system and treatment. The number and percentage of subjects with adverse events by maximum severity of adverse event will be tabulated by body system and preferred term with a breakdown by treatment.

Columbia-Suicide Severity Rating Scale (C-SSRS)

All C-SSRS results will be listed by subject and visit/time.

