## 7 Discontinuation and study completion

### 7.1 Discontinuation of study treatment

Subjects may voluntarily discontinue study treatment for any reason at any time. They may be considered withdrawn if they state an intention to withdraw, fail to return for visits, or become lost to follow-up for any other reason. If a subject withdrawal occurs for any reason, the investigator must make every effort to determine the primary reason for a subject's withdrawal from the study and record this information on the CRF.

The investigator must discontinue study treatment for a given patient if, on balance, he/she believes that continuation would be detrimental to the patient's well-being.

Study treatment **must** be discontinued under the following circumstances:

- Subject withdraws consent
- Pregnancy

Discontinuation of investigational treatment will be at the discretion of the Investigator, under the following circumstances:

- Emergence of the following adverse events:
  - Symptomatic hypotension or orthostatic hypotension (hypotensive or orthostatic blood pressure readings must be confirmed on repeat measurement within 30 minutes) that requires medical intervention.
  - Systolic blood pressure <80 mm Hg (must be confirmed on repeat measurement after 30 minutes)
  - Symptomatic severe hypertension (e.g., a systolic blood pressure >180 mmHg or a diastolic blood pressure >120 mmHg) that requires medical intervention
- Any of the following laboratory abnormalities:
  - A reproducible and persistent (> 24 hours) increase in serum creatinine from baseline of >0.3 mg/dL unless the benefit/risk assessment supports continuing study treatment. A renal event leading to patient discontinuation should be followed up until event resolution (Serum Cr within 10% of baseline), or event stabilization (Serum Cr level with  $\pm 10\%$  variability over last 6 months).
- Use of prohibited treatment as per [Section 5.3](#)
- Any other protocol deviation that results in a significant risk to the subject's safety

The appropriate personnel from the site and Novartis will assess whether investigational treatment should be discontinued for any subject whose treatment code has been broken inadvertently for any reason.

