## **7.4 Study Stopping rules**

The study will be stopped if any of the following criteria are met and no further dosing will be taken pending a full safety review:

- 2 severe AEs are reported
- 3 subjects experience a persistent (> 24 hours) and reproducible increase in serum creatinine >0.3 mg/dL from baseline
- 3 or more subjects experience a similar AE which is assessed as either moderate or severe in intensity

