## 9.4 Renal safety monitoring

Renal events are defined as one of the following:

- confirmed (after  $\geq 24\text{h}$ ) increase in serum creatinine of  $\geq 25\%$  compared to baseline during normal hydration status
- new onset ( $\geq 1+$ ) proteinuria, hematuria or glucosuria; or as a
- doubling in the urinary albumin-creatinine ratio (ACR) or urinary protein-creatinine ratio (PCR) (if applicable).

The following two categories of abnormalities/adverse events have to be considered during the course of the study:

- Serum creatinine triggers that will require follow up and repeat assessments of the abnormal laboratory parameter
- Urine dipstick triggers that will require follow up and repeat assessments of the abnormal laboratory parameter

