**Table 9-3 Specific Renal Alert Criteria and Actions**

Renal Event	Actions
Serum creatinine increase 25 – 49% compared to baseline	Confirm 25% increase after 24-48h Follow up within 2-5 days
Serum creatinine increase $\geq 50\%$ compared to baseline	Follow up within 24-48h if possible Consider drug interruption Consider patient hospitalization /specialized treatment
Albumin- or Protein-creatinine ratio increase $\geq 2$ -fold	Confirm value after 24-48h Perform urine microscopy
Albumin-creatinine ratio (ACR) $\geq 30\text{ mg/g}$ or $\geq 3\text{ mg/mmol}$ ;	Consider drug interruption / discontinuation
New dipstick proteinuria $\geq 1+$ Protein-creatinine ratio (PCR) $\geq 150\text{ mg/g}$ or $>15\text{ mg/mmol}$	
New dipstick glucosuria $\geq 1+$ not due to diabetes	Blood glucose (fasting) Perform serum creatinine, ACR
New dipstick hematuria not due to trauma	Urine sediment microscopy Perform serum creatinine, ACR
Document contributing factors: co-medication, other co-morbid conditions, and additional diagnostic procedures performed in the CRF	
Monitor patient regularly (frequency at investigator's discretion) until one of the following:	
Event resolution: (sCr within 10% of baseline or protein-creatinine ratio within 50% of baseline)	
Event stabilization: sCr level with $\pm 10\%$ variability over last 6 months or protein-creatinine ratio stabilization at a new level with $\pm 50\%$ variability over last 6 months.	

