##### **Clinical laboratory evaluations**

All laboratory data will be listed by treatment, subject, and visit/time and if normal ranges are available abnormalities will be flagged. Summary statistics will be provided by treatment and visit/time.

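### The protocol's creatinine criteria are changes from baseline, but the planned laboratory outputs flag only out-of-range values and do not count patients meeting those criteria by arm

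*SAP*

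**What the plan says.** **The protocol's criteria.**
- Section 9.4 counts as a renal event a confirmed "increase in serum creatinine of" at least 25%, "compared to baseline during normal hydration status". Dipstick and albumin- or protein-creatinine ratio criteria sit beside it; this point concerns creatinine only.
- Table 9-3 sets actions for "Serum creatinine increase 25 – 49% compared to baseline" and for a rise of at least 50%.
- Section 7.1 leaves discontinuation to the investigator's discretion for "A reproducible and persistent (> 24 hours) increase in serum creatinine from baseline of >0.3 mg/dL unless the benefit/risk assessment supports continuing study treatment".
- Section 7.4 stops the study, pending a safety review, if "3 subjects experience a persistent (> 24 hours) and reproducible increase in serum creatinine >0.3 mg/dL from baseline".

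**The analysis.** SAP 8.1.2 states: "All laboratory data will be listed by treatment, subject, and visit/time and if normal ranges are available abnormalities will be flagged". It adds a further listing for any subject with an abnormal value, and summary statistics by treatment and visit. Protocol 11.5.2 has the same rule: "if normal ranges are available abnormalities will be flagged. Summary statistics will be provided by treatment and visit/time". Neither mentions change from baseline for laboratory data, the 25%, 50% or 0.3 mg/dL thresholds, or a count of patients reaching them.

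**Context.** Safety is a primary objective in both documents. Protocol 2.1 gives adverse events and serious adverse events as its endpoints; SAP 7.1 also places laboratory measurements among the first primary variables. SAP 7.1.2 does ask for change from baseline for ambulatory blood pressure, so the plan names that summary where it is wanted.

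**The concern.** The flagging rule and the renal criteria are on different scales. One asks whether a value is outside a population range; the others ask how far the patient has moved from baseline. A patient can meet a renal criterion without a single flagged value, and a mean by visit hides a few such patients.

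Every patient takes an ARB and a diuretic with the study drug, and protocol 10.3 provides no data monitoring committee. The planned tables are therefore the visible prespecified comparison of renal safety between arms. Followed as written, they would not give the number of patients per arm with a confirmed 25% rise, a 50% rise or a rise above 0.3 mg/dL. Someone would have to derive those counts afterwards, choosing the baseline value, the confirmation rule and the handling of repeat samples once the data are known.

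**Working it through.** The plan gives no figure on this point to reproduce, and the sample size text is redacted. The check is threshold algebra.

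**Inputs.** Thresholds of 25%, 50% and 0.3 mg/dL (protocol 9.4, Table 9-3, 7.1, 7.4). Arm sizes of 40 placebo and 20 per dose, so 40 pooled LHW090 (protocol 11.4.2). The creatinine ULN is not in the documents; 1.0 to 1.4 mg/dL is an assumed range.

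**1. When does a qualifying rise stay unflagged?** For baseline B:
- A rise of fraction r stays in range if B × (1 + r) ≤ ULN, that is B ≤ ULN / (1 + r). For 25%: 1 / 1.25 = 0.80 × ULN. For 50%: 1 / 1.5 = 0.67 × ULN. These multiples hold whatever the ULN is.
- A rise just over 0.3 mg/dL stays in range if B is below ULN − 0.3.

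| Assumed ULN (mg/dL) | 25% rise unflagged up to B = | 50% rise unflagged up to B = | Rise just over 0.3 unflagged below B = |
|---|---|---|---|
| 1.0 | 0.80 | 0.67 | 0.70 |
| 1.2 | 0.96 | 0.80 | 0.90 |
| 1.4 | 1.12 | 0.93 | 1.10 |

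**2. One patient.** Assume a ULN of 1.2 mg/dL and a move from 0.80 to 1.15 mg/dL. The rise is 0.35 mg/dL, and 0.35 / 0.80 = 44%. If confirmed and persistent, it meets the renal event definition and the creatinine threshold in 7.1 and 7.4. No value is flagged.

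**3. Does the mean by visit show it?** If k of n patients rise by d, the arm mean moves by k × d / n.
- Three of 40 rising 0.3 mg/dL: 3 × 0.3 / 40 = 0.0225 mg/dL, while 3 / 40 = 7.5% of the arm.
- The same three in one 20-patient dose arm: 3 × 0.3 / 20 = 0.045 mg/dL, while 3 / 20 = 15% of the arm.

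Three patients with rises just above 0.3 mg/dL are the number that section 7.4 requires.

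**4. Is one threshold enough?** The relative and absolute criteria coincide at B = 0.3 / 0.25 = 1.2 mg/dL. Below that baseline the 25% criterion is reached first; above it, the 0.3 mg/dL criterion. They select different patients, so each needs its own count.

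**5. Repeat samples.** Table 9-3 asks for confirmation after 24-48 hours. Such repeats will mostly fall between the scheduled visits, and the SAP does not say how they enter a summary by visit.

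**The case against.** The strongest reply is that nothing is hidden, and much of it stands.

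- **All laboratory values are listed by treatment and subject.** True: the rises can be derived later. What is missing is the prespecified flag and count.
- **Adverse event reporting can catch a rise.** Protocol 9.1 lets investigators use change from baseline when judging clinical significance, and 8.4.4 requires relevant deviations to be discussed with the sponsor and repeated. Such events are tabulated by arm. This is a real route, but it rests on judgement and does not apply the numerical thresholds.
- **Discontinuations are listed with reasons, and the sponsor must count rises above 0.3 mg/dL to operate 7.4.** True. But discontinuation is discretionary, so patients who continue do not appear there. The stopping rule is not stated by arm and does not cover the 25% event.
- **Summary statistics may include the maximum.** Possibly, but the highest value need not belong to the patient with the largest rise.
- **Other outputs cannot be seen.** The SAP refers to table shells that are not provided, and its safety graphics text is redacted. The finding applies to the visible text; the laboratory paragraph itself shows no redaction.

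A reader might infer more than the documents support. They do not show that a renal signal would be reported as absent, since the listings and adverse event tables remain. They do not make a 25% rise a ground for stopping a patient or the study: Table 9-3 asks for confirmation and follow-up at 25-49%, and at 50% or more for drug interruption only to be considered. Nor can one say that the sponsor identified renal harm as a specific risk of LHW090, because the risk text is redacted.

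**Conclusion.** The point holds for the laboratory outputs. The visible plan flags creatinine against the normal range, while the protocol's creatinine criteria are all relative to baseline, and no planned laboratory table counts patients on that scale by arm. A 25% rise goes unflagged from any baseline up to 0.80 × ULN and a 50% rise from any baseline up to 0.67 × ULN; neither multiple needs an assumption about the ULN. The mg/dL limits rest on the assumed ULN range. How many patients would be affected is unknown, because the documents give no baseline creatinine distribution.

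This is a gap in prespecified safety reporting in a non-confirmatory study with descriptive safety analysis. It does not affect the efficacy inference or any clinical rule. It is worth correcting because SAP 7.1 makes laboratory measurements a primary variable and the correction is cheap.

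**What to change.** In SAP 8.1.2 and protocol 11.5.2:

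1. Summarise absolute and percent change from baseline in serum creatinine by treatment and visit, and state which value is the baseline.
2. Tabulate n (%) of patients for each dose, pooled LHW090 and placebo with a post-dose rise of at least 25%, at least 50% and more than 0.3 mg/dL. Count each threshold separately, once for any occurrence and once for rises confirmed on repeat. Include unscheduled values and state which repeats count as confirmation.
3. Flag these patients in the laboratory listing, next to the normal-range flags.

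The thresholds are the protocol's existing ones in 7.1, 7.4, 9.4 and Table 9-3; none is changed, and no management rule is affected. The cost is SAP wording, one extra table and a listing flag from creatinine values already collected. No new assessments are needed.
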